Pharmacokinetic (PK) samples as well as sitting BP and pulse should be taken from pre-dose until 24 hours after the first dose (for detailed time of PK samples, BP and pulse see Table 2). During the early morning PK sampling the patient should be encouraged to stay in supine position until their normal waking time

The patient will eat a standardized meal approximately one hour after each dose of AZD3355 and at the same time points during the different study periods. The meals (food and liquid) will be standardized primarily regarding fat content and pH. The patient should be encouraged to complete the meal. If not possible, the same amount should be eaten at each meal during

each study period. During the stay in the clinic the patients should be encouraged to move around to mimic normal activities as much as possible.

Day 2: In the morning of day two, the last PK sample and a reduced safety lab screen will be collected. Sitting BP and pulse is measured before the patients leaves the clinic.

The active questioning for specific symptoms will take place again (see Section [6.4.3.2](#)) before the patient leaves in the mornings after the impedance is completed, but before the catheter is removed.

No antacids are allowed 24 hours before and during the treatment period (due to interference with pH measurement). The 4 study periods will be separated by a washout period of 7-28 days.

Adverse events (AEs) will be recorded after drug administration at Visit 2 throughout the study.

Table 2 Study period procedures

Time post dose (h:min)	Clock Time^a (h:min)	PK blood sample^b (No)	Blood pressure and pulse monitoring^c	Activity
Day 1				
Pre-dose	07:00	1	Sitting, supine and standing after 1 min	BP, pulse, dECG, orthostatic test, reduced laboratory screen, PGx ^e urine sample for drug abuse screen ^d Placement of impedance/pH catheter
0:00	08:00			Active question specific symptoms Drug/placebo administration Start of impedance/pH recording
0:30	08:30	2		
1:00	09:00			Breakfast
1:30	09:30	3		
2:00	10:00	4	Supine + standing after 1 min	dECG, orthostatic test
2:30	10:30	5		
4:00	12:00	6	Sitting	
4:30	12:30			Lunch
8:00	16:00	7	Sitting	Snack
12:00	20:00	8	Sitting	Drug/placebo administration
12:30	20:30	9		
13:00	21:00			Evening meal
13:30	21:30	10		
14:00	22:00	11	Sitting	
14:30	22:30	12		
Day 2				
16:00	00:00	13		
21:00	05:00	14		

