13. Pregnant or breast feeding females.
14. Need for concomitant medication with:
 - Drugs that may interfere with the pharmacodynamic effect of Investigational Product (eg, Baclofen, pure GABA, supplements containing GABA).
 - Drugs that by their mode of action may alter gastrointestinal symptoms, with exception of the PPI used in the study, (eg, H₂ receptor antagonists, sucralfate, alginates, tegaserod, domperidone, metoclopramide, erythromycin), drugs with significant anticholinergic effect (eg, anticholinergics used in gastro-intestinal disorders; anticholinergics used for Parkinson's disease; anticholinergics used for urine bladder disorders; tricyclic antidepressants).
 - Drugs that may cause mucosal damage in the GI tract:
 - Non-steroid anti-inflammatory drugs (NSAIDs), or cyclooxygenase-2 (COX-2) inhibitors, more than 2 days/week
 - Acetylsalicylic acid (ASA) >162 mg
 - Bisphosphonates
 - Antineoplastic drugs
 - Drugs that may prolong the QT interval, see [Appendix G](#).
 - Drugs that have a narrow therapeutic window (eg, warfarin, digoxin, phenytoin, carbamazepine).

15. The following laboratory exclusion criteria based on laboratory samples from visit 1 assessed at visit 2:
- S-creatinine >1.2 x ULN
 - AST or ALT >2 x ULN
 - Bilirubin >1.5 x ULN
 - S-potassium below the lower reference range
 - S-magnesium below the lower reference range
 - Other clinically significant electrolyte imbalances as judged by the investigator
16. Plasma donation within one month of screening or blood donation or any blood loss equivalent to the amount of a blood donation during the 3 months prior to screening.
17. Any other condition which in the opinion of the investigator would render the patient unsuitable for inclusion in the study.

Exclusion criteria for the optional participation in the pharmacogenetics part of the study are described in [Appendix D](#).

Procedures for withdrawal of incorrectly enrolled patients see Section [5.4](#).

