5.9 Discontinuation of investigational product

Patients may be discontinued from investigational product (IP) in the following situations:

- Patient decision. The patient is at any time free to discontinue treatment, without prejudice to further treatment
- Adverse Event
- Severe non-compliance to study protocol
- Not fulfilling study specific inclusion/exclusion criteria
- Need for disallowed medication
- Inability to perform impedance/pH measurements or manometric evaluation

- Development of any study specific criteria:
 - Patient experiencing symptoms of paraesthesia daily for at least 7 consecutive days, see Section 6.4.3.1
 - Patient experiencing syncopal episode from any cause or if a patient describes an adverse event of pre-syncope or dizziness as severe. Orthostatic dizziness provoked during testing would not automatically discontinue a patient unless this continued without provocation from orthostatic testing (eg, when getting up from bed).
 - Patient with a corrected QTc (QTcF) ≥ 500 ms
 - Patients requiring a change in dose or to stop treatment of their prescribed PPI
 - Patients who develops abnormalities in laboratory values:
 - S-creatinine $> 1.2 \times$ ULN
 - AST or ALT $> 2 \times$ ULN
 - Bilirubin $> 1.5 \times$ ULN
 - S-potassium below the lower reference range
 - S-magnesium below the lower reference range
 - other clinically significant electrolyte imbalances as judged by the investigator

Patients who discontinue from investigational product may not continue in the study. See Section 5.9.1 for procedures for discontinuation.

5.9.1 Procedures for discontinuation of a patient from investigational product and from the study

A patient that decides to discontinue investigational product will always be asked about the reason(s) and the presence of any adverse events. If possible, they will be seen and assessed by an investigator(s) and perform a follow-up visit (Visit 6). Adverse events will be followed up (see Sections 6.4.3 and 6.4.4) and the patient should return diary cards and study drug.

If a patient is withdrawn from study, see Section 5.10.

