6.4.5.1 Full laboratory screen

Blood samples (~12 ml) and urine samples for a full laboratory screen will be collected at the pre-entry visit within 21 days prior to the first study period and at the follow-up visit

5-10 days after the last study period. The full laboratory screen will include the variables in [Table 3](#) below.

Table 3 Full laboratory screen

Test	Unit	Comment
Clinical Chemistry		
S- Aspartate aminotransferease (ASAT)	µkat/L (U/L)	
S- Alanine aminotransferase (ALAT)	µkat/L (U/L)	
S- Alkanine phosphatase (ALP)	µkat/L (U/L)	
S- Total bilirubin	µmol/L	
S- Albumin (Alb)	g/L	
S- Creatine Kinase (CK)	µkat/L (U/L)	
S- Creatinine (Creat)	µmol/L	
S- Urea	mmol/L	
S- Sodium (Na)	mmol/L	
S- Potassium (K)	mmol/L	
S- Magnesium (Mg)	mmol/L	
S- Calcium (Ca)	mmol/L	
P- Glucose	mmol/L	Fasting
S- C-Reactive Protein (CRP)	µmol/L	
Clinical Haematology		
B- Haemoglobin (Hb)	g/L	
B- Erythrocyte Particle Concentration	10 ¹² /L	
B- Erythrocyte Mean cell Volume (Ery-MCV)	L/L (%)	
B- Mean Cell Haemoglobin Concentration (MCHC)	10 ⁹ /L	
B- Leukocyte Particle Concentration (LPC)	10 ⁹ /L	
B- Platelet Particle Concentration (PPC)	10 ⁹ /L	
Urinalysis (dip-stick)		
U- Protein		
U-Glucose		
U-Haemoglobin		
U-Pregnancy test		If applicable

For blood volume see Section [7.1](#).

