6.4.5.2 Reduced laboratory screen

Blood samples (~8 ml) and urine samples for a reduced laboratory screen will be collected before first dose at each study period and 12 hours after the last dose. The reduced laboratory screen will include the variables in [Table 4 below](#).

Table 4 Reduced laboratory screen

Test	Unit	Comment
Clinical Chemistry		
S- Aspartate aminotransfese (ASAT)	µkat/L (U/L)	
S- Alanine aminotransferase (ALAT)	µkat/L (U/L)	
S- Alkanine phosphatase (ALP)	µkat/L (U/L)	
S- Total bilirubin	µmol/L	
S- Creatine Kinase (CK)	µkat/L (U/L)	
S- Creatinine (Creat)	µmol/L	
S- Sodium (Na)	mmol/L	
S- Potassium (K)	mmol/L	
S- Calcium (Ca)	mmol/L	
P- Glucose	mmol/L	Fasting
Clinical Haematology		
B- Haemoglobin (Hb)	g/L	
B- Erythrocyte Particle Concentration	10 ¹² /L	
B- Leukocyte Particle Concentration (LPC)	10 ⁹ /L	
B- Platelet Particle Concentration (PPC)	10 ⁹ /L	
Urinalysis (dip-stick)		
U- Protein		
U-Glucose		
U-Haemoglobin		

For blood volume see Section [7.1](#).

Drugs of abuse

Urine will be tested for drugs of abuse at screening (Visit1) and repeated randomly once more during the study. The following substances will be tested: benzodiazepines, cocaine, and/or metabolites, amphetamines, tetrahydrocannabinol (THC), opiates, methamphetamines (including ecstasy), phencyclidine (PCP) and barbiturates. The result of the drug screen will be recorded in the patients medical records and recorded in the CRF, but will not be included

in the analysed data. If a patient test positive for drugs of abuse they will be excluded from entering or continuing in the study.

HIV and hepatitis screens

Testing for the HIV antibody, HBsAg, and anti-HCV (~8 ml) is to be performed on all patients at screening (Visit 1) only. If a test result is positive, the patient will not be allowed to proceed in the study. The results of the HIV and hepatitis screens will be documented in the patient medical records and recorded in the CRF but will not be included in the analysed data.

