6.4.6 Physical examination

A physical examination will be performed at visit 1 and visit 6 (pre-entry and follow-up) and include an assessment of the following:

- General appearance
- Skin
- Head and neck (including ears, eyes and throat)
- Lymph nodes
- Thyroid
- Abdomen
- Musculo-skeletal (including extremities)
- Cardiovascular, respiratory and neurological systems
- Neurological systems (including cranial nerves and reflexes)

6.4.7 dECG

A 12-lead dECG will be taken at visit 1 (screening), visit 2-5 (both pre-dose and 2 hours after the first dose), visit 6 (follow-up) and any other time the investigator deems necessary for safety during the dosing period. The 12 lead dECGs will be obtained after the patient has been lying down for at least 10 minutes.

The dECGs will be reviewed by the investigator or a qualified cardiologist who will judge the overall interpretation as normal or abnormal. If abnormal, it will be decided as to whether or not the abnormality is clinically significant or not. The evaluation will be recorded in the appropriate sections of the CRF.

All dECGs will be transferred to a central reader for evaluation for general evaluation of ECG trends.

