6.9 Health economics (Not Applicable)

7. BIOLOGICAL SAMPLING PROCEDURES

7.1 Volume of blood

The total volume of blood that will be drawn from each patient in this study is as follows:

Table 5 Volume of blood to be drawn from each patient

Assessment	Sample volume (mL)	No. of samples	Total volume (mL)
Safety Full laboratory screen, HP	12	2	24
Reduced laboratory screen	8	8	64
Hepatitis B, C, HIV	8	1	8
Pharmacokinetic	2	60	120
Pharmacogenetics ^a	10	1	10
Total			226

^a Only if the patient is participating in the optional PGx part of the study, see [Appendix D](#).

By discretion of the investigator additional blood samples may be taken for patient safety reasons outside the scope of this protocol.

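### Low magnesium is a named discontinuation criterion, but no scheduled magnesium test falls between Visit 1 and the last dose

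*Protocol*

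**What the plan says.** Section 5.9 sets study-specific grounds for discontinuing investigational product. One group covers patients who develop laboratory abnormalities. It names creatinine, AST or ALT, bilirubin, potassium and "S-magnesium below the lower reference range", and adds a general item for other electrolyte imbalances that the investigator judges clinically significant.

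Two laboratory panels are scheduled:

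- **Full screen (Section 6.4.5.1, Table 3).** It includes magnesium. It is drawn at the pre-entry visit and at follow-up, "5-10 days after the last study period".
- **Reduced screen (Section 6.4.5.2, Table 4).** The text says that "a reduced laboratory screen will be collected before first dose at each study period and 12 hours after the last dose". Its electrolytes are sodium, potassium and calcium; magnesium is not listed.

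Table 1 agrees: full screen at Visits 1 and 6, reduced screen at Visits 2 to 5. Exclusion criterion 15 in Section 4.2 also uses low magnesium and is introduced as "The following laboratory exclusion criteria based on laboratory samples from visit 1 assessed at visit 2", so entry relies on the Visit 1 value. Section 7.1 adds: "By discretion of the investigator additional blood samples may be taken for patient safety reasons outside the scope of this protocol".

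**The concern.** The criterion is about abnormalities that arise after entry, so it needs a value obtained after entry and before dosing is complete. The schedule provides none. The Visit 1 value has already served for eligibility, and the Visit 6 value arrives when there is no study drug left to stop.

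The magnesium rule is the sponsor's own, used both at entry and on study. Section 1.4 reports that a thorough QT study did not exclude a QTc effect, although the upper confidence limits passed 10 msec only slightly, at three time points. The protocol does not say why magnesium was chosen, so the link to QTc is an inference. Whatever the reason, as scheduled the on-study half of the rule operates only if someone thinks to order the test.

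**Working it through.** **1. Reproduce the sampling plan in Table 5.**

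- Full screens: Visit 1 + Visit 6 = 2, at 12 mL = 24 mL.
- Reduced screens: 4 periods × 2 = 8, at 8 mL = 64 mL.
- Hepatitis and HIV: 8 mL. Pharmacokinetics: 15 × 4 = 60 samples, at 2 mL = 120 mL. Pharmacogenetics: 10 mL.
- Total: 24 + 64 + 8 + 120 + 10 = 226 mL, as Table 5 states.

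The schedule is therefore read correctly: 2 + 8 = 10 safety samples per patient.

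**2. Set the named criteria against the two panels.**

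| Analyte in Section 5.9 | Table 3 (Visits 1, 6) | Table 4 (Visits 2–5, twice per period) |
|---|---|---|
| Creatinine | yes | yes |
| AST | yes | yes |
| ALT | yes | yes |
| Bilirubin | yes | yes |
| Potassium | yes | yes |
| Magnesium | yes | **no** |

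Five of the six are measured twice in every period; magnesium is the only one missing. It is in 2 of 10 scheduled safety samples, in 0 of the 8 at Visits 2 to 5, and in none between Visit 1 and the last dose.

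**3. Age of the last scheduled magnesium value on the final dosing day.**

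Age = gap from Visit 1 to Visit 2 + three washouts. Section 3.1 puts the pre-entry visit within 21 days of the first study day, and says of the washouts: "The 4 study periods will be separated by a washout period of 7-28 days".

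- Minimum: 0 + 3 × 7 = 21 days.
- Maximum: 21 + 3 × 28 = 105 days.
- If each washout is counted from the end of a one-day period, add up to 3 days: 24 to 108.

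The longest interval from Visit 1 to the Visit 6 value is about 105 + 10 = 115 days, again ignoring those extra days.

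**4. What adding magnesium to Table 4 would achieve.**

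Scheduled magnesium tests at Visits 2 to 5 would rise from 0 to 8. The samples from periods 1 to 3, 2 × 3 = 6, could be reviewed before a later period's dose, because periods are at least 7 days apart. The seventh, pre-dose in period 4, is drawn at about 07:00 for a first dose at 08:00 (Table 2), and nothing requires its result before dosing. The eighth follows the last dose.

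**The case against.** The strongest reply is that this is a consistency point of low weight:

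- **Permissive wording.** Section 5.9 says patients may be discontinued, and some of its other grounds also apply only if something comes to light. Section 7.1 allows extra safety samples.
- **Little exposure and no signal.** Treatment is two doses on each of four separate days, one of them placebo, so at most three drug days precede the final dosing day. Section 1.4 reports no clinically relevant chemistry findings apart from mild liver enzyme increases at higher repeated doses (400 mg bid). Nothing in the protocol suggests that the drug lowers magnesium.
- **Filters and backstops.** Section 4.2 excludes low magnesium at Visit 1, a history of clinically significant electrolyte imbalance, heart disease, QTcF of 450 ms or more, and need for QT-prolonging drugs. Digital ECGs are recorded at "visit 2-5 (both pre-dose and 2 hours after the first dose", with a discontinuation criterion at QTcF of 500 ms or more.
- **Another remedy.** The mismatch could be closed by deleting the magnesium line from Section 5.9.

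Most of this stands as a limit on the risk, and the upper figure of 105 days takes the longest value of every window. None of it supplies the missing value. Discretion needs a result to act on, and Section 7.1 places the extra samples outside the protocol. The re-check provision in Section 6.4.5 helps only for analytes already measured. The ECGs are a partial backstop, since none is scheduled after the evening dose, and the QTcF limit is a separate criterion. Deleting the line would make the text consistent by removing a safeguard that the sponsor chose to include, so it is the weaker repair.

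**Conclusion.** The point holds. A named safety criterion has no scheduled test that could trigger it while doses are still to be given: 0 of 8 samples at the dosing visits include magnesium, and the last scheduled value is about 21 to 105 days old at the final dosing day. The day counts take the washout as the interval between study days; the other reading adds up to 3 days.

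The practical risk is limited and the primary dose-response estimate is not affected. It is a mismatch between a rule and its measurement schedule, worth correcting because the correction is so small. Nothing in the protocol explains the omission, and as magnesium alone of the six named analytes is missing, it looks like an oversight.

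**What to change.** Add serum magnesium to Table 4, so that results from periods 1 to 3 can be reviewed before the first dose of the next period. The 07:00 pre-dose sample should not be counted on to protect the 08:00 dose on the same day unless the protocol also requires the result before dosing.

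The cost is one line in Table 4 and one extra assay on each of 8 samples per patient, at most 8 × 27 = 216 assays for the 27 randomised patients. No visit or blood draw is added. Blood volume stays the same if the local laboratory confirms that magnesium can be run on the existing sample of about 8 mL; the protocol does not say so, and this is an assumption.

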5.10 Withdrawal from study

Patients are at any time free to withdraw from the study (investigational product and assessments), without any prejudice to further treatment (withdrawal of consent). Such patients will always be asked about the reason(s) and the presence of any adverse events. If

possible they will be seen and assessed by an Investigator. Adverse events will be followed up (see Sections 6.4.3 and 6.4.4) and the patient should return diary cards and study drug.

For enrolled but not randomised patients, the following modules in the CRF must be entered at a minimum:

- Demography
- Eligibility criteria, incl. RESQ-7
- AE
- If SAE criteria was fulfilled, the AE and SAE modules must be completed
- Study termination
- Investigators signature

6. COLLECTION OF STUDY VARIABLES

6.1 Recording of data

A paper Case Report Form will be used for data collection and query handling. The investigator will ensure that data are recorded on the CRF as specified in the study protocol and in accordance with the instructions provided.

The investigator ensures the accuracy, completeness, and timeliness of the data recorded and of the provision of answers to data queries according to the Clinical Study Agreement. The investigator will sign the completed CRFs. A copy of the completed paper CRFs will be archived at the study site.

The diary card completed by the patient during the 24-hours impedance/pH measurements will not be entered into the CRF. The diary will be analysed together with the data from the data logger by the central reader of impedance/pH data, see Section 6.3.1.1.

6.2 Data collection and enrolment

6.2.1 Screening assessments

Each patient will complete the following assessments during the screening.

- Obtaining written informed consent prior to any study specific procedures
- RESQ-7 (see Section 6.5.1)
- Demography data - date of birth, sex, race

- Medical and surgical history, including medication and PPI use
- GI history, IBS symptoms and history of paraesthesia, syncope or orthostatic reaction
- Complete physical examination (see Section 6.4.6)
- Vital signs (Supine resting SBP and DBP, pulse)
- Height (cm) and weight (kg) (for BMI calculation)
- 12-lead dECG
- Blood and urine samples for standard clinical chemistry, haematology assessments, hepatitis C antibody (HIV antibody, Hepatitis B surface Antigen (HBsAg), hepatitis C antibody (anti-HCV) and PK samples, and drugs of abuse screen (see Section 6.4.5). If applicable, a urine pregnancy test and/or HP serology. Genetic sampling is optional.

6.3 Efficacy

6.3.1 Efficacy variable

6.3.1.1 Impedance/pH measurements

Esophageal impedance/pH monitoring will be performed using a Sleuth[®] Multi-channel Intraluminal Impedance Ambulatory system (Sandhill Scientific, Inc; Highlands Ranch, CO). The system includes a portable data logger with impedance/pH amplifiers and a catheter, 2.13 mm outer diameter, with two antimony pH sensors that will be placed 5 cm above the LES and 10 cm below the LES as well as eight impedance electrodes at 2, 4, 6, 8, 10, 14, 16 and 18 cm above the tip of the electrode. Each pair of electrodes measures impedance over a 2 cm segment at 3, 5, 7, 9, 15 and 17 cm above the LES. Before and after the recordings, the pH electrodes will be calibrated using standard buffers of pH 7 and pH 1. The catheters will be passed transnasally under topical anaesthesia and positioned in relation to the LES as located by a manometric recording. After 24-hours continuous recording, the impedance/pH catheters will be removed.

For acquisition of pH data, the data logger measures and stores the potential differences between recording and reference sensors in the esophagus. The impedance measurements allow detection of gastroesophageal reflux based on changes in resistance (Ohms) to alternating electrical current flow <6 microamperes at a frequency of 1-2 kHz between a series of ring sensors on the probe, when liquid and/or gas bolus moves between them. The six impedance and pH signals are recorded at 50 Hz on a 128 MB Compact Flash card for further computer analysis. The impedance/pH data will be downloaded on a personal computer and then stored as the original acquisition file in Bioview[™] Autoscan[™] format and will also be converted to an deidentified ACII file format on a CD, which will be sent to the central reader for analysis. All data and CDs will be sent back to the study team at AstraZeneca.

During the 24 hours of ambulatory impedance/pH measurement, the patient will be using the data logger and a diary card to record meal intake and periods in supine position, as well as GERD symptoms. Time is recorded on the device and the corresponding event is described in the paper diary on which the patient will be recording the type of GERD symptoms. The diary card can be seen in [Appendix H](#). A copy of the de-identified diary card will also be sent to the central reader for uploading and confirmation of event marker recordings.

Data will be analysed visually and with the support of a dedicated software (Bioview Analysis[®], Version 5.5.4, Sandhill Scientific, Inc.) Analysis will include identification and characterization of individual reflux events, measurements of clearance times (pH and bolus), calculation of symptom and change in position in association to reflux episodes, measurement of esophageal exposure to reflux of various composition and pH as well as measurements of gastric pH.

The data will be analysed by one central reader blinded to treatment allocation, [name] at Northwestern University Medical School, Division of Gastroenterology, Chicago, USA. The purpose of utilizing a central reader is to have a consistent assessment and analysis of measurements for all study impedance/pH data.

The central reader will determine the validity of the pH recordings based on the following criteria established for evaluability: A minimum of 20 hours of impedance/pH recording must be obtained in order to have evaluable data. Data points that will be excluded are: pH<0 or >9, flat recording artifact associated with loss of signal or drift artifact. The recording must not have technical failures of the pH recording and must not have 1 continuous hour or more with pH data outside the reference range. If the recording is less than 20 hours due to these technical issues the data is not evaluable.

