- Orthostatic tests performed in healthy volunteers given single doses between 65 and 1800 mg and either as single or repeated doses 65 to 800 mg has provoked positive test with or without dizziness. Apart from provoked dizziness, there are some reports of postural dizziness and one event of presyncope with an accompanied sinus arrest (sinus pause of 8.2 seconds) in phase I.

- Paraesthesia is an identified adverse drug reaction to AZD3355 both in healthy volunteers and patients. The reported symptoms were mainly mild to moderate in intensity, reversible, short lasting and usually started and ended within one hour after dosing. Paraesthesia has not been associated with any abnormal neurological findings of sensory or motor function on physical examination.
- No clinically relevant findings have been seen in clinical chemistry or haematology laboratory screen or urine analyses in any of the studies completed so far, except for mild liver enzyme increases after repeated dosing of higher doses than proposed in this study (400 mg bid).

The benefit to the subjects participating in this study is limited to the thorough medical investigation they will be given (physical examination, ECG, laboratory tests etc) before entering the study. The patients will be followed during the study period and at the follow-up visit. The safety of the patients has been considered when deciding the inclusion- and exclusion criteria, the proposed restrictions and the criteria for discontinuation. No adverse effects on fertility or embryofetal development have been seen in non-clinical studies. However, since no data exist on embryofetal development in humans, women of childbearing potential must use an adequate highly effective contraceptive method to be eligible for studies with AZD3355.

The methods for assessing reflux episodes and pH may be uncomfortable to the subject and involves 24 hours testing. Mild adverse events related to 24 hour catheter impedance/pH monitoring may be observed, eg. less than 5% of subjects may have nasal irritation and very rarely, patients may develop epistaxis.

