5.5 Blinding and procedures for unblinding the study

5.5.1 Methods for ensuring blinding

All packaging and labelling will be done in such way as to ensure blinding. The capsules for AZD3355 and placebo will appear identical. All patients, study personnel, AstraZeneca personnel, as well as the central reader of impedance/pH data will be blinded to the treatment given during the 4 treatment periods.

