Appendix H
Diary Card for 24-hours impedance pH measurement

24-Hour Ambulatory Impedance-pH Patient Diary Sheet - D9120C00032

Patient: _____
 ID #: _____

Date: _____
 Start time: ____:____ am/pm
 End Time: ____:____ am/pm

MEALS / SNACKS

Press once	BEGIN TIME	Press once	END TIME	NOTES
	____:____ am/pm		____:____ am/pm	
	____:____ am/pm		____:____ am/pm	
	____:____ am/pm		____:____ am/pm	
	____:____ am/pm		____:____ am/pm	
	____:____ am/pm		____:____ am/pm	
	____:____ am/pm		____:____ am/pm	
	____:____ am/pm		____:____ am/pm	

SLEEP / LYING DOWN

Press once	BEGIN TIME	Press once	END TIME	NOTES
	____:____ am/pm		____:____ am/pm	
	____:____ am/pm		____:____ am/pm	
	____:____ am/pm		____:____ am/pm	

SYMPTOMS

Press once	TIME	NOTES	Press once	TIME	NOTES
	____:____ am/pm			____:____ am/pm	
	____:____ am/pm			____:____ am/pm	
	____:____ am/pm			____:____ am/pm	
	____:____ am/pm			____:____ am/pm	
	____:____ am/pm			____:____ am/pm	
	____:____ am/pm			____:____ am/pm	
	____:____ am/pm			____:____ am/pm	
	____:____ am/pm			____:____ am/pm	
	____:____ am/pm			____:____ am/pm	

MEDICATIONS

	____:____ am/pm		____:____ am/pm		____:____ am/pm		____:____ am/pm
---	-----------------	---	-----------------	---	-----------------	---	-----------------

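### The central reader marks reflux episodes with the patient's symptom entries available, which can bias the Symptom Index

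*Protocol*

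**What the plan says.** Section 6.3.1.1 sets out how the recordings are read. On method: "Data will be analysed visually and with the support of a dedicated software." On the reader: "The data will be analysed by one central reader blinded to treatment allocation." Section 5.5.1 repeats that the reader is blinded.

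The reader also receives the diary. Section 6.3.1.1: "A copy of the de-identified diary card will also be sent to the central reader for uploading and confirmation of event marker recordings." Section 6.1 puts the two sources side by side: "The diary will be analysed together with the data from the data logger by the central reader of impedance/pH data."

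The diary holds meals, lying-down periods and GERD symptoms. Times are stored by the logger, and "the corresponding event is described in the paper diary on which the patient will be recording the type of GERD symptoms." The form in Appendix H has a press-once marker for each entry, free-text notes columns for meals, lying down and symptoms, and a medications row.

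Section 11.1.2 gives numeric impedance and pH criteria for each type of episode. Section 11.1.3 defines two association measures:

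- **SI:** the share of symptoms with a reflux event within 2 minutes before or after; 50% or more counts as positive.
- **SAP:** calculated from two-minute periods of pH recording, with reflux defined as pH<4 for at least 5 seconds.

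The link between reflux and symptoms is a secondary objective (Section 2.2).

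**The concern.** An association measure is interpretable only if its two components are assessed independently. Here one person decides whether a borderline impedance change is a reflux event, with the symptom entries available at the same time. Under the SI definition, that decision settles whether a nearby symptom is reflux positive. De-identifying the diary removes the patient's identity and leaves the symptom times and types in place.

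The criteria in Section 11.1.2 are numeric, but visual reading leaves judgement in applying them: the baseline, artefact, propagation and, for gas, the absence of swallowing. A reader who has seen a symptom mark cannot set it aside, and no later analysis can separate true association from its influence on scoring.

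The SI also carries weight that the SAP cannot take over. The objective covers weakly acidic and weakly alkaline reflux, and a pH<4 rule does not detect either.

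**Working it through.** The plan gives no figure for reader influence, so there is nothing to reproduce. I sized the possible effect under labelled assumptions.

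**Inputs from the protocol**

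- SI window of 2 minutes either side, cut-off 50% (11.1.3).
- In the earlier 65 mg bid crossover study, 24-hour geometric mean ratio 0.61 (1.3) and geometric mean on active 30.6 (12.3). Implied placebo mean: 30.6 / 0.61 = 50.2.
- Paraesthesia in 5% of patients in the 4-week studies and 24.4% of healthy volunteers (1.4).
- 27 randomised patients with 3 active periods each: at most 81 active recordings.

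**Assumptions**

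- *q*: share of reflux-negative symptoms upgraded because the symptom time is known.
- *Sp*, *Sa*: symptoms per recording on placebo and on active.
- *f*: share of active recordings with a note that reveals treatment.
- *u*: fraction by which the reader undercounts those recordings.

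**Step 1. SI.** SI′ = SI + q(1 − SI).

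| True SI | q = 5% | q = 10% | q = 20% |
|---|---|---|---|
| 0.40 | 0.43 | 0.46 | 0.52 |
| 0.45 | 0.48 | 0.505 | 0.56 |

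Modest upgrading can therefore cross the cut-off. Few symptoms make the SI coarse: with 4 symptoms, one changed call moves it by 1/4 = 25 points, for example from 25% to the 50% cut-off. That step shows how sensitive the measure is; it does not estimate reader bias.

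**Step 2. Primary count, same mechanism.** Suppose 60% of symptoms are reflux negative and each upgrade adds one episode. The ratio becomes (30.6 + 0.6·q·Sa) / (50.2 + 0.6·q·Sp).

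- 10 symptoms on placebo, 5 on active, q = 10%: 30.9 / 50.8 = 0.609.
- Same counts, q = 20%: 31.2 / 51.4 = 0.607.
- Extreme, 20 against 5, q = 20%: 31.2 / 52.6 = 0.594.
- Extreme, 20 against 20, q = 20%: 33.0 / 52.6 = 0.628.

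Against 0.610, the ordinary cases barely move, and the extremes go in opposite directions.

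**Step 3. Primary count, revealing notes.** Suppose every paraesthesia case is written down and recognised: 81 × 0.05 ≈ 4 to 81 × 0.244 ≈ 20 recordings. The ratio becomes 0.61 × (1 − u)^f.

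| f | u = 5% | u = 20% |
|---|---|---|
| 0.05 | 0.608 (inhibition 39.2%) | 0.603 (39.7%) |
| 0.244 | 0.602 (39.8%) | 0.578 (42.2%) |

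From 39.0%, inhibition rises by 0.2 to 3.2 points.

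**The case against.** **Scoring is not by eye alone.** Software supports it and Section 11.1.2 fixes numeric thresholds. This bounds the reader's discretion without removing it, so the point stands only as something that can bias the SI, not as a demonstrated bias.

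**The SAP does not depend on scored impedance events.** This stands. The exposure is mainly in the SI.

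**The reading order may be set in a reader manual.** Section 6.3.1.1 refers to no such manual, and Section 6.1 states that the two sources are analysed together. Marking first is not forbidden, but the workflow as written points the other way.

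**The stronger reading.** A reader might infer that the diary unblinds the reader and so threatens the primary count. "Paraesthesia is an identified adverse drug reaction to AZD3355 both in healthy volunteers and patients", and Section 1.4 adds that it usually starts and ends within an hour of dosing, so it would fall inside the recording. The protocol does not support going that far:

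- The diary asks for GERD symptoms. Paraesthesia and dizziness go to CRF modules (6.4.3 to 6.4.3.2), which are not among the material sent to the reader.
- A leak needs a patient to volunteer a non-GERD note and the reader to act on it.
- Section 5.1 allows paracetamol for minor symptoms in any period, so an entry for it does not identify active drug.
- The 5% and 24.4% are per-person rates, from up to 4 weeks of dosing and from a programme with single doses up to 1800 mg. Applying them to one-day periods stacks assumptions. With the 14 + 16 + 16 + 14 = 60 evaluable active recordings planned in Section 12.3, the 4 to 20 becomes about 3 to 15.

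Occasional hints remain possible, which justifies no more than a minor precaution.

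**Conclusion.** The point holds for the SI. The workflow in Sections 6.1 and 6.3.1.1 does not keep event scoring independent of symptom timing, and the SI is built directly on the match between the two. Upgrading 10% of reflux-negative symptoms takes an SI of 45% past the cut-off, and upgrading 20% does the same from 40%. Those upgrade rates are assumptions; the protocol gives no data on reader influence.

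The SAP is largely protected by its pH rule, though only for acid reflux. For the primary total count, no consistent bias appears from knowing symptom times. The unblinding route through free text is speculative and worth at most about 3 points of inhibition when every assumption is stacked against the design. It should not be presented as a failure of the reader's blinding.

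**What to change.** State in Section 6.3.1.1, and align Section 6.1, that reading is done in two stages:

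1. The reader marks and locks all reflux episodes with only meal and lying-down times available. Those times are needed for the upright and supine split, so the diary cannot simply be withheld in full. The symptom event markers on the data logger are hidden or not yet loaded; masking the paper diary alone is not enough, because symptom presses are stored on the device.
2. Symptom times and types are then merged, and SI and SAP are computed with no change to locked episodes.

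As a minor precaution, mask the medications row and any non-GERD notes on the diary copy sent to the reader.

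The cost is an extra file-preparation and upload step for up to 27 × 4 = 108 recordings, plus some site judgement about which notes describe GERD symptoms. The reader, the recordings and the data collected stay the same.
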